8.2 Statistical Analysis Plan

Statistical Analysis Plan

All patients who received any dose of the study agent will be included in the analysis for efficacy and safety. Drop out of patients will count as failure for the efficacy analysis. Demographic/clinical characteristics (i.e. including duration of response) and safety data of the patients will be summarized using descriptive statistics such as mean, standard deviation, median and range. For the primary efficacy analysis, we will estimate the ORR (cohort 1) and ORR (cohort 2) for the combination treatment, along with the 95% credible interval. For the efficacy of cohort 1, a sample size of 20 patients ensures a posterior 95% credible interval for ORR of (0.06, 0.37), if the trial is not terminated early, under the assumption of a 20% ORR. For the efficacy of cohort 2, a sample size of 20 patients ensures a posterior 95% credible interval for ORR of (0.48, 0.85), if the trial is not terminated early, under the assumption of a 70% ORR. The association between ORR and patient's clinical characteristics will be

Product: MK-3475

60

Protocol/Amendment No.: 2016-0343 Amendment 2

examined by Wilcoxon's rank sum test or Fisher's exact test, as appropriate. Toxicity type, severity and attribution will be summarized for each patient using frequency tables. The distribution of time-to-event endpoints (EFS and OS) will be estimated using the method of Kaplan and Meier. Comparisons of time-to-event endpoints by important subgroups will be made using the log-rank tests. Paired t-tests will be used to determine the immunological and molecular changes in the peripheral blood and bone marrow from baseline to the time of response, and to the time of disease progression.

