5.2 Trial Treatments

The treatment to be used in this trial is outlined below in Table 2.

Patients will be treated with the combination of azacitidine and MK3475. The dose of azacitidine will be 75 milligrams per meter squared IV or SC daily for 7 consecutive days following a standard administration guidelines for this compound. MK3475 will be administered at a dose of 200 milligrams every three weeks starting on Cycle 1 Day 1 and will continue every three weeks thereafter independent of azacitidine dosing. A cycle will be considered as 4 weeks and will be based upon the azacitidine dosing schedule. Cycles will be repeated for as long as possible unless evidence of significant toxicity or progression to AML (defined by more than 30% blasts in the marrow), unless there is frank proliferation in peripheral blood (in the opinion of the treating physician), or if it is not safe for the patient. Patients will receive the first course of therapy without interruption regardless of the degree of myelosuppression. Patients can continue to receive therapy indefinitely until one of the criteria outlined below occurs. After the first course of therapy the interval between cycles of therapy can be spaced out at the discretion of the treating physician, but will otherwise be scheduled as close to possible to the initial 4 weeks. If there is evidence of prolonged myelosuppression defined by absolute neutrophil count of less than $1 \times 10^9/\text{dl}$ and a platelet count of less than $30 \times 10^9/\text{dL}$ for more than 42 days with evidence of hypocellular marrow (defined as marrow cellularity of less than 5%), subsequent courses of the azacitidine will be given at the next lower dose after the counts have recovered to an ANC of more than $1 \times 10^9/\text{dL}$ and platelet more than $30 \times 10^9/\text{dL}$. Cycles will be repeated as long as possible until toxicity or lack of response for at least 6 cycles of combination therapy.

In the absence of treatment delays due to early trial termination as described in Section 5.10, treatment may continue indefinitely until one of the following criteria applies:

Product: Pembrolizumab

20

Protocol/Amendment No.: 2016-0343 Amendment 3.4

1-Clinically significant progressive disease

2-Possibility of undergoing allogeneic stem cell transplant

3-Clinical significant intercurrent illness that prevents further administration of treatment

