5.8 Subject Withdrawal/Discontinuation Criteria

Subjects may withdraw consent at any time for any reason or be dropped from the trial at the discretion of the investigator should any untoward effect occur. In addition, a subject may be

Product: Pembrolizumab

Protocol/Amendment No.: 2016-0343 Amendment 3.4

withdrawn by the investigator or the Sponsor if enrollment into the trial is inappropriate, the trial plan is violated, or for administrative and/or other safety reasons. Specific details regarding discontinuation or withdrawal are provided in Section 7.1.4 – Other Procedures.

A subject must be discontinued from the trial for any of the following reasons:

- The subject or legal representative (such as a parent or legal guardian) withdraws consent.
- Confirmed radiographic disease progression

Note: A subject may be granted an exception to continue on treatment with confirmed radiographic progression if clinically stable or clinically improved

- Unacceptable adverse experiences
- Intercurrent illness that prevents further administration of treatment
- Investigator's decision to withdraw the subject
- The subject has a confirmed positive serum pregnancy test
- Noncompliance with trial treatment or procedure requirements
- The subject is lost to follow-up
- Completed 24 months of uninterrupted treatment with pembrolizumab or 35 administrations of study medication, whichever is later.

Note: 24 months of study medication is calculated from the date of first dose. Subjects who stop pembrolizumab after 24 months may be eligible for up to one year of additional study treatment if they progress after stopping study treatment with Medical Monitor approval

- Administrative reasons

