7.1.4 Other Procedures

7.1.4.1 Withdrawal/Discontinuation

When a subject discontinues/withdraws prior to trial completion, all applicable activities scheduled for the final trial visit should be performed at the time of discontinuation. Any adverse events which are present at the time of discontinuation/withdrawal should be followed in accordance with the safety requirements outlined in Section 7.2 - Assessing and Recording Adverse Events. Subjects who a) attain a CR or b) complete 24 months of treatment with pembrolizumab may discontinue treatment. After discontinuing treatment following assessment of CR, these subjects should return to the site for a Safety Follow-up Visit (described in Section 7.1.5.3.1) and then proceed to the Follow-Up Period of the study (described in Section 7.1.5.4).

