7.1.5.4 Follow-up Visits

Subjects who discontinue trial treatment for a reason other than disease progression will move into the Follow-Up Phase and should be assessed about every 6-8 weeks (\pm 7 days) as clinically indicated to monitor disease status. Every effort should be made to collect information regarding disease status until the start of new anti-neoplastic therapy, disease progression, death, end of the study or if the subject begins retreatment with pembrolizumab. Information regarding post-study anti-neoplastic treatment will be collected if new treatment is initiated.

Survival Follow-up

Once a subject experiences confirmed disease progression or starts a new anti-cancer therapy, the subject moves into the survival follow-up phase and should be contacted by telephone every 12 weeks to assess for survival status until death, withdrawal of consent, or the end of the study, whichever occurs first.

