8.0 STATISTICAL ANALYSIS PLAN

8.1 Statistical Analysis Plan Summary

This is a Phase II open-label study designed to evaluate the safety and efficacy of the combination of MK3475 and 5-azacitidine in patients with MDS. Two different patient groups (hypomethylating failure group and previously untreated MDS group) will be studied. Each cohort will be composed of N=20 patients. Accrual will be parallel for each patient group.

The primary efficacy outcome for each cohort is the overall response rate (ORR) defined as CR + PR + hematological improvement (HI). Overall response will be assessed after 6 cycles of treatment; cycle length is 28 days. A maximum of 20 patients will be enrolled in each cohort (total for study N=40).

Hypomethylating failure MDS cohort

The target ORR with the experimental treatment is 20%. There is no standard treatment for this patient population, we use a null ORR of 5%. The regimen of the experimental treatment will be considered worthy of further investigation if it elicits an increase in ORR to 20% with acceptable toxicity. A >30% therapy related non-hematological grade 3/4 toxicity rate is considered unacceptable. Thus, interim monitoring rules, assuming the prior distributions below, were constructed that meet the following two conditions,

- 1) Stop if $\text{Prob}\{p(\text{ORR}, E) < p(\text{ORR}, H) + 0.15 \mid \text{data}\} > 0.99$, or
- 2) Stop if $\text{Prob}\{p(\text{TOX}, E) > 0.30 \mid \text{data}\} > 0.95$,

where $p(\text{ORR}, E)$ and $p(\text{TOX}, E)$ are the true ORR and toxicity rates for the combination treatment, and $p(\text{ORR}, H)$ is the true ORR rate of the standard treatment. The first rule provides for stopping the study if the data suggest that it is unlikely (i.e., probability < 1%) that ORR rate of the experimental treatment is greater than the ORR rate of standard treatment by 15%. The second condition will stop the study early if excessive therapy-related non-hematological grade 3/4 toxicity (>30%) is highly probable (i.e., probability >95%) for the experimental treatment. Monitoring for toxicity and futility will start with the first patient, and cohort size of 5.

The monitoring rule for the toxicity rate, based on these assumptions and monitoring conditions above is found in Table 8. For example, accrual will cease if 4 or more patients experience toxicities among the first 5 patients.

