Table 8. Stop accrual if the number of drug-related non-hematological grade 3/4 toxicities is greater than or equal to indicated (i.e., # patients with toxicities) among the number of patients evaluated				
# patients evaluated	5	10	15	20
# patients with toxicities	4-5	6-10	8-15	Always stop

Monitoring the ORR rate, based on the above assumptions and monitoring conditions is found in Table 9. For example, accrual will cease if no patients experience an overall response within 6 cycles in the first 10 patients treated.

Table 9. Stop accrual if the number with response is less than or equal to indicated (i.e., # patients with overall response) among the number of patients evaluated			
# patients evaluated	5	10-15	20
# patients with response	Never	0	Always stop

Multc Lean Desktop (version 2.1.0) was used to generate the toxicity and futility stopping boundaries and the OC table (Table 10). In order to utilize the software for the design, a response constant rate of 5% and beta (0.1, 1.9) prior were assumed for the standard treatment response rate and experimental treatment response prior distribution, respectively. A delta 15% was assumed. In addition, a 30% toxicity constant rate and beta (0.6, 1.4) priors were assumed for the standard treatment toxicity rate and experimental treatment toxicity prior distribution, respectively.

The probability of stopping the study early if the true ORR of the combination treatment was 20% and the true toxicity rate was 30% was 18%. Probabilities of stopping early for high true toxicity rates (i.e., 50%) were 82% when the true ORR was 5% and 61% when true ORR rate was 20%.

Table 10. Operating characteristics for simultaneous monitoring response and toxicity rates for patients treated with combination treatment		
True Toxicity Rate	True ORR	Prob(stop the trial early)
0.10	0.05	0.5990
	0.10	0.3491
	0.15	0.1973
	0.20	0.1079
	0.25	0.0569

Table 10. Operating characteristics for simultaneous monitoring response and toxicity rates for patients treated with combination treatment

True Toxicity Rate	True ORR	Prob(stop the trial early)
0.20	0.05	0.6040
	0.10	0.3573
	0.15	0.2075
	0.20	0.1192
	0.25	0.0688
0.30	0.05	0.6326
	0.10	0.4037
	0.15	0.2647
	0.20	0.1828
	0.25	0.1360
0.40	0.05	0.7085
	0.10	0.5268
	0.15	0.4166
	0.20	0.3516
	0.25	0.3145
0.50	0.05	0.8230
	0.10	0.7126
	0.15	0.6456
	0.20	0.6062
	0.25	0.5836

Previously untreated MDS cohort

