The target ORR with the experimental treatment is 70%, assuming the standard treatment ORR is 50%. The regimen of the experimental treatment will be considered worthy of further investigation if it elicits an increase in ORR to 70% with acceptable toxicity. A >30% therapy related non-hematological grade 3/4 toxicity rate is considered unacceptable. Thus, interim monitoring rules, assuming the prior distributions below, were constructed that meet the following two conditions,

- 3) Stop if $\text{Prob}\{p(\text{ORR}, E) < p(\text{ORR}, H) + 0.20 \mid \text{data}\} > 0.95$, or
- 4) Stop if $\text{Prob}\{p(\text{TOX}, E) > 0.30 \mid \text{data}\} > 0.95$,

where $p(\text{ORR}, E)$ and $p(\text{TOX}, E)$ are the true ORR and toxicity rates for the combination treatment, and $p(\text{ORR}, H)$ is the true ORR rate of the standard treatment. The first rule provides for stopping the study if the data suggest that it is unlikely (i.e., probability < 5%) that ORR rate of the experimental treatment is greater than the ORR rate of standard treatment by 20%. The second condition will stop the study early if excessive therapy-related

non-hematological grade 3/4 toxicity (>30%) is highly probable (i.e., probability >95%) for the experimental treatment. Monitoring for toxicity and futility will start with the first patient, and cohort size of 5.

The monitoring rule for the toxicity rate, based on these assumptions and monitoring conditions above is found in Table 11. For example, accrual will cease if 4 or more patients experience toxicities among the first 5 patients.

Table 11. Stop accrual if the number of drug-related non-hematological grade 3/4 toxicities is greater than or equal to indicated (i.e., # patients with toxicities) among the number of patients evaluated

# patients evaluated	5	10	15	20
# patients with toxicities	4-5	6-10	8-15	Always stop

Monitoring the ORR rate, based on the above assumptions and monitoring conditions is found in Table 12. For example, accrual will cease if 1 patients experience an overall response within 6 cycles in the first 5 patients treated.

Table 12. Stop accrual if the number with response is less than or equal to indicated (i.e., # patients with overall response) among the number of patients evaluated

# patients evaluated	5	10	15	20
# patients with response	0-1	0-4	0-7	Always stop

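### Does counting drop-outs as efficacy failures, with drop-out undefined, leave the primary response rate open to more than one answer?

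*Combined protocol and SAP*

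**What the plan says.** Section 8.2 includes every patient who received any dose in the efficacy analysis and adds "Drop out of patients will count as failure for the efficacy analysis". It gives no definition of drop-out. It plans a 95% credible interval for ORR in each cohort of 20.

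Section 8.1 defines ORR as CR, PR or hematological improvement and says "Overall response will be assessed after 6 cycles of treatment; cycle length is 28 days". The monitoring examples use a different preposition. For the HMA-failure cohort, "accrual will cease if no patients experience an overall response within 6 cycles in the first 10 patients treated"; for the untreated cohort, "accrual will cease if 1 patients experience an overall response within 6 cycles in the first 5 patients treated".

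On leaving treatment or the trial:

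- Section 5.8 says a subject may "be dropped from the trial at the discretion of the investigator should any untoward effect occur".
- Section 5.2 lists, among the reasons to end treatment, "2-Possibility of undergoing allogeneic stem cell transplant".
- Section 7.1.4.1 says "Subjects who a) attain a CR or b) complete 24 months of treatment with pembrolizumab may discontinue treatment", with a safety visit and the follow-up period afterwards. Section 5.8.1 discourages stopping therapy after CR unless there is a medical reason or the patient so decides.
- Section 7.1.5.4 says "Subjects who discontinue trial treatment for a reason other than disease progression will move into the Follow-Up Phase". Section 5.8 has the same provision.

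**The concern.** The sentence governs the numerator of the primary endpoint and can be read in two ways. Marrow is examined late in cycles 1 and 3 (Section 6.1, footnote c), so a response can be on record well before cycle 6. A patient may then stop for transplant, for toxicity or after CR. If stopping treatment is dropping out, that responder becomes a failure; if dropping out means leaving the trial, the response stands. The two timing phrases add a second choice: status at the end of cycle 6, or best response up to then. The plan also does not say whether the drop-out rule applies at the interim looks.

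The trial is open label and uncontrolled, so a reading settled late could be settled with outcomes in view. With 20 patients per cohort, each rescored patient is worth 1/20 = 5 percentage points.

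**Working it through.** **The plan's own figures.** Inputs are the priors and rules in Section 8.1. Section 8.2 gives the 20% target to cohort 1, while Section 2.0 makes cohort 1 the untreated group, so cohorts are named by population here. The posterior is Beta(a + x, b + n − x), with equal-tailed 95% limits.

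- HMA failure, prior Beta(0.1, 1.9), 4/20: Beta(4.1, 17.9) gives (0.057, 0.369). The plan states (0.06, 0.37).
- Untreated, prior Beta(1, 1), 14/20: Beta(15, 7) gives (0.478, 0.854). The plan states (0.48, 0.85).
- Tables 8, 9, 11 and 12 follow from the stated posterior cuts. All 25 cells of Table 10 and all 25 of Table 13 reproduce within 0.00005, with looks at 5, 10 and 15 and with response and toxicity independent.

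So no stated number is wrong, and the question is only one of definition.

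**Which departures are drop-outs.** Taking each route in turn:

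1. *Transplant.* Section 5.2 lists it as an end of treatment. If it counts as new anti-cancer therapy, Section 7.1.5.4 moves the patient to survival follow-up, which is still within the trial.
2. *CR.* Section 7.1.4.1 sends those who stop after CR to a safety visit and then the follow-up period.
3. *Toxicity or other non-progression reasons.* Sections 5.8 and 7.1.5.4 continue disease-status follow-up until progression, new therapy, withdrawal of consent or loss.

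None of the three is an exit from the trial. What is left for drop-out to mean is withdrawal of consent, loss to follow-up or removal from the study.

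**Timing.** Both monitoring examples count a response occurring within 6 cycles. Section 5.2 likewise refers to lack of response for at least 6 cycles. Assessment after 6 cycles is then the time at which that window is evaluated.

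**Size if the strict reading were taken.** One responder rescored in the final analysis:

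| Cohort | Count | 95% interval | Rescored | 95% interval |
|---|---|---|---|---|
| HMA failure | 4/20 | (0.057, 0.369) | 3/20 | (0.033, 0.310) |
| Untreated | 14/20 | (0.478, 0.854) | 13/20 | (0.430, 0.819) |

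The HMA-failure interval moves across the 5% null, but the plan has no rule based on excluding 5%. The posterior probability that ORR exceeds 5% is 0.984 at 4/20 and 0.926 at 3/20.

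Suppose the strict reading also applied at interim looks and a share f of responders were lost. The values of f are assumptions, since the documents give none. Scored ORR is the true ORR times (1 − f).

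| f | Untreated: scored ORR | Futility stop | HMA failure: scored ORR | Futility stop |
|---|---|---|---|---|
| 0 | 70% | 8.4% | 20% | 10.7% |
| 5% | 66.5% | 13.6% | 19% | 12.2% |
| 10% | 63% | 20.3% | 18% | 13.7% |
| 20% | 56% | 38.2% | 16% | 17.5% |

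The HMA-failure column is (1 − p)^10, for example 0.8^10 = 0.1074. The whole stop probability falls at the 10-patient look, because a cohort that passes it has at least one response and cannot then show 0/15. If the rule applies only at the final analysis, the stop probabilities stay at 8.4% and 10.7% for every f.

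**The case for a change.** The strongest argument is that the sentence is undefined rather than merely conservative. Section 5.8 mixes leaving the trial with stopping treatment: the same list covers withdrawn consent, unacceptable adverse experiences and completed pembrolizumab treatment. A literal reader could call a responder removed for toxicity in cycle 4 a drop-out and score a failure. At the boundary one patient can matter. In the untreated cohort, posterior P(ORR < 0.70) is 0.930 at 2/5 but 0.989 at 1/5, against a cut of 0.95. In the HMA-failure cohort, P(ORR < 0.20) is 0.897 at 1/10 but 0.997 at 0/10, against 0.99.

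The missing definition stands, and so does the arithmetic. The inference that the result is therefore open does not. The strict reading must treat stopping treatment as leaving the trial, against the follow-up provisions. To affect monitoring, it must also override the within-6-cycles count that the stopping examples use. Its error would lower the response rate, against the experimental regimen. Scoring as failures those who leave with no documented response is ordinary conservative practice in an uncontrolled trial. Best response by cycle 6 and status at cycle 6 are both acceptable endpoints, and preferring one does not show a fault in the other.

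Sections 5.8.1 and 7.1.4.1 differ on stopping therapy after CR and must be reconciled. That is a separate matter: under the ordinary reading a documented CR counts whichever text prevails.

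**Conclusion.** This is a gap that analysts would fill sensibly, so no change to the plan follows. Read with the follow-up sections, drop-out means leaving the trial, a response documented within 6 cycles counts, and treated patients without one are failures. On that reading the stated intervals, boundaries and operating characteristics all stand.

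Under the strict reading each affected responder costs 5 percentage points of ORR, always downward. The rise in the futility stop from 8.4% to 38.2% (untreated) needs three things together: the strict reading, its use at interim looks, and a 20% loss of responders. The first runs against the protocol's other sections, the second is nowhere stated, and the third is an assumption. The conclusion rests on the ordinary meaning of drop-out and on the within-6-cycles wording governing both monitoring and the final count.

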The End of Treatment and Follow-up visit procedures are listed in Section 6 (Protocol Flow Chart) and Section 7.1.5 (Visit Requirements). After the end of treatment, each subject will be followed for 30 days for adverse event monitoring (serious adverse events will be collected for 90 days after the end of treatment as described in Section 7.2.3.1). Subjects who discontinue for reasons other than progressive disease will have post-treatment follow-up for disease status until disease progression, initiating a non-study cancer treatment, withdrawing consent or becoming lost to follow-up. After documented disease progression each subject will be followed by telephone, every 12 weeks, for overall survival until death, withdrawal of consent, or the end of the study, whichever occurs first.

Product: Pembrolizumab

Protocol/Amendment No.: 2016-0343 Amendment 3.4

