c. Bone marrow biopsy and/or aspiration collected at screening, between days 22 to 28 of Cycles 1 and 3, then every 3 cycles thereafter, additional bone marrow evaluations could be performed as clinically indicated. Bone Marrow Correlatives will be collected at the same time.

d. Correlative studies blood collection will be collected: at screen, prior to each of MK3475 dose during the first 3 cycles, at time of best morphological response and at progression

e After Cycle 1, azacitidine may be administered and routine laboratory tests may be performed/ordered by patient's local physician, if the patient is not scheduled to return to MD Anderson on those days.

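### Duration of response is summarised by mean, SD, median and range, with no stated way to handle responses still ongoing; Kaplan-Meier is named only for EFS and OS

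*Combined protocol and SAP*

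**What the plan says.** Duration of response appears once, in a parenthesis in section 8.2, as an example of a clinical characteristic: "including duration of response) and safety data of the patients will be summarized using descriptive statistics such as mean, standard deviation, median and range". Later in the same section: "The distribution of time-to-event endpoints (EFS and OS) will be estimated using the method of Kaplan and Meier". Duration of response is not on that second list.

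Other sections touch on the quantity without defining it:

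- Section 4.2.4.1 adopts the IWG 2006 response criteria by reference and reproduces no rule on duration.
- Section 8.1 defines ORR as CR, PR or hematological improvement and says "Overall response will be assessed after 6 cycles of treatment; cycle length is 28 days". Its notes to the stopping tables count responses occurring within six cycles.
- The footnote to the section 6.1 flow chart places marrows "between days 22 to 28 of Cycles 1 and 3, then every 3 cycles thereafter".
- Section 5.8 continues disease follow-up, for patients who stop for reasons other than progression, "for disease status until disease progression, initiating a non-study cancer treatment, withdrawing consent or becoming lost to follow-up". Section 7.1.5.4 asks for "disease status until the start of new anti-neoplastic therapy, disease progression, death, end of the study or if the subject begins retreatment with pembrolizumab". The lists differ: only the second names death, study end and retreatment.
- Section 5.2 lists "Possibility of undergoing allogeneic stem cell transplant" among the reasons for ending treatment, and section 7.1.4.1 says "Subjects who a) attain a CR or b) complete 24 months of treatment with pembrolizumab may discontinue treatment".
- Section 8.2 treats patients who drop out as failures in the efficacy analysis, without a date and without mentioning duration.

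**The concern.** A response that is ongoing when observation stops has a known minimum length and an unknown total. A mean, SD, median and range have no place for that. An analyst following section 8.2 must either enter the observed length as if the response had ended, or leave such patients out. Both choices shorten the reported durations, and the second selects the short responses. Because the plan picks neither, the choice would be made after the data are seen.

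At stake is how durable responses appear, mainly in the previously untreated cohort, where the target ORR of 70% implies about 14 responders of 20. Section 3.1 makes clinical activity a primary objective and section 4.1 gives delaying failure as a reason for front-line combinations, so readers will look at this number. No decision rule in the plan uses it.

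**Working it through.** The plan states no figure for duration of response, so there is none to reproduce. The question is how far the named summaries drift when some responses are cut off.

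**From the documents.** Section 1.0 gives 24 months of enrolment in a 36-month trial, so follow-up from entry runs from 36 − 24 = 12 months to 36 months. The same table gives 36 months as duration of participation, so follow-up of 36 months for all is shown as well. Expected responders at target: 20 × 0.70 = 14 (previously untreated) and 20 × 0.20 = 4 (HMA failure).

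**Assumed, because the documents are silent.** Exponential durations with true median m of 9, 12 or 18 months; onset at month 4; uniform entry; no cut-off except study end. Follow-up from onset, C, is then uniform from 8 to 32 months, or 32 months for all.

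**Formulas.** With λ = ln 2 / m:

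- True mean = 1/λ.
- Share cut off = (e^(−8λ) − e^(−32λ)) / (24λ).
- Plain mean, cut-off responses counted as complete = (1 − share cut off)/λ. With 32 months for all it is (1 − e^(−32λ))/λ.
- Plain median t solves 2^(−t/m) × P(C > t) = 0.5, where P(C > t) = (32 − t)/24 for t between 8 and 32.

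**At m = 12.** λ = 0.0578 and 1/λ = 17.3. Share cut off = (0.630 − 0.158)/1.386 = 0.34. Plain mean = 17.3 × 0.66 = 11.4. With 36 months for all: 17.3 × (1 − 0.158) = 14.6. Plain median: at t = 10.28, 0.552 × 0.905 = 0.50.

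| True median | True mean | Cut off | Plain mean | Plain mean, 36 months for all | Plain median | Median of completed responses only |
|---|---|---|---|---|---|---|
| 9 | 13.0 | 25% | 9.8 | 11.9 | 8.6 | 6.1 |
| 12 | 17.3 | 34% | 11.4 | 14.6 | 10.3 | 6.9 |
| 18 | 26.0 | 48% | 13.5 | 18.4 | 12.6 | 7.8 |

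Moving onset between 2.8 and 5.5 months (end of cycle 3 to just before the end of cycle 6) changes the plain median at a true 12 from 10.8 to 9.6.

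**When the median is safe.** With study end as the only cut-off, the plain median is right as long as m does not exceed the shortest follow-up from onset: 12 − 4 = 8 months, or 36 − 4 = 32 months if all are followed for 36. Other cut-offs remove that protection. If 20% of responders were cut off by month 12 at a constant rate (an assumption), that hazard is −ln(0.8)/12 = 0.0186. The plain median at a true 12 becomes ln 2/(0.0578 + 0.0186) = 9.1, even with 36 months for all.

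**Noise.** With 14 responders, 12 to 36 months of follow-up and a true median of 12, the simulated 10th to 90th percentile range is 7.2 to 13.8 months for the plain median and 7.3 to 19.9 for the Kaplan-Meier median.

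**Start date.** Six cycles end at day 6 × 28 = 168. Dating response there rather than at a cycle 3 marrow (about day 84) or a cycle 1 marrow (about day 28) shortens a duration by 84 or 140 days. This applies only if response is dated by marrow, which the plan does not say; hematological improvement also counts as response.

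**The case against.** The case for leaving this alone has several parts.

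- The list of statistics is introduced as examples, so Kaplan-Meier is permitted. That stands, but a permitted method is not a planned one.
- A reader might infer that the trial has no definition of duration at all. The documents do not support that: IWG 2006 is adopted by reference and its content cannot be checked here. The supportable statement is that the protocol text gives none.
- A reader might infer that the start date alone moves durations by three to five months. That holds only under marrow dating, and counting responses within six cycles fits an earlier date equally well.
- A reader might infer that the reported median will be badly wrong. At assumed true medians of 9 to 12 months the median bias is smaller than the sampling noise; it stands out only at about 18 months, a value no section supports. The distortion of the mean is larger, and it persists with 36 months of follow-up for all.
- Censoring dropouts could conflict with the section 8.2 rule that dropouts are failures. This stands, and the fix must address it.
- With about 4 responders in the HMA-failure cohort, Kaplan-Meier adds little. This also stands.

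**Conclusion.** The point holds as a minor matter of descriptive analysis. Section 8.2 assigns to duration of response summaries that cannot represent an ongoing response, and the protocol text supplies no start, end or censoring rule. Under the stated assumptions, at a true median of 12 months, the plain mean is about 5.9 months too low (17.3 − 11.4), or 2.7 too low (17.3 − 14.6) with 36 months of follow-up for all. The plain median is about 1.7 too low (12 − 10.3), and unbiased with 36 months for all only if nothing but study end cuts responses off. These sizes rest on assumed durations and onset, not on anything the documents report. A reader might take this as undermining the efficacy conclusion; it does not. ORR, sample size, credible intervals and stopping rules are unaffected. The open start date and the unstated handling of transplant are missing detail and would not carry the point on their own.

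**What to change.** A cheap improvement to section 8.2:

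1. Move duration of response to the Kaplan-Meier sentence: by cohort, among responders, from first documented response to relapse, progression or death, censored at the last disease assessment.
2. State that the rule treating dropouts as failures applies to ORR, or say how it applies to duration.
3. State whether transplant, new therapy and pembrolizumab retreatment censor the duration or count as events in this analysis.
4. Where responders are few, as expected in the HMA-failure cohort, make a listing of individual durations with an ongoing-response flag the main output.

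The cost is a few sentences. Disease-status follow-up is already planned in sections 5.8 and 7.1.5.4, and no visit, treatment or sample size changes.

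The downside is wide or open intervals. In simulation with 14 responders and 12 to 36 months of follow-up, the upper 95% log-log limit for the median could not be estimated in 35%, 61% and 88% of trials at true medians of 9, 12 and 18 months. The median itself was not reached in 0.5%, 3.3% and 19%. With 36 months for all, the upper limit was missing in 2.6%, 17% and 62%. With 4 responders and a true median of 6 months it was never estimable; counting a curve that falls to zero as reaching the limit lowers this to about 32%.
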